## Abstract

### Objective(s) and Hypotheses:

Osteoarthritis (OA) is a degenerative joint disease which severely limits mobility and is associated with moderate to severe amounts of pain and discomfort. Ankle OA is strongly associated with a prior injury (vs. “wear and tear” which is more common at other joints). Prior injuries to the bones surrounding the ankle joint may cause the joint to become misaligned over time, and the cartilage surfaces to wear abnormally fast – likely contributing to OA.

The motion of the bones at the ankle joint (and therefore their alignment) is very difficult to measure. Clinically, a static (non-moving) standing x-ray is used to diagnose the presence and severity of ankle misalignment; however this does not capture misalignment during movement which may result in missed opportunities for diagnosis and early intervention with non-invasive treatment.

This study has three aims:

1) measure bone motion and alignment using an x-ray technique that captures bone motion in 3D during walking (dynamic measurement with our biplane fluoroscope)

- Hypothesis 1: During gait, there are different tibio-talar kinematics between OA participants with static varus alignment, OA participants with static valgus alignment, and controls.

2) determine if the single static clinical image technique is accurate enough to diagnose ankle misalignment 100% of the time, and completely capture the severity of misalignment

- Hypothesis 2: Some static neutrally aligned OA participants will exhibit varus or valgus tibio-talar misalignment when measured dynamically using biplane fluoroscopy.

3) determine if an inexpensive medical device, a shoe insert (wedged orthotic) is capable at restoring alignment.

- Hypothesis 3: OA participants with static (varus/valgus) tibio-talar misalignment will exhibit reduced misalignment when walking with (lateral/medial) wedge insoles.
- Hypothesis 4: OA participants with static neutral alignment, but with dynamic (varus/valgus) tibiotalar misalignment will exhibit reduced misalignment when walking with (lateral/medial) wedge insoles

### Research Design & Methodology:

Up to 120 participants with ankle OA (up to 40 with varus misalignment, up to 40 with valgus misalignment, up to 40 with neutral alignment) and up to 30 participants without ankle OA will be enrolled. Participants will be men and women, age 18-80 years, who are able to stand and walk for at least one hour without significant difficulty. Participants will undergo a series of radiological measurements including: a standard x-ray from the hips down, a set of x-rays of the legs, a CT scan from the knees down, up to 80 fluoroscopic images while walking or

standing. Participants will do the fluoroscopic trials with and without wedged shoe insoles. The radiological measurements will be used to address the aims outlined above.

At the end of this study we hope to: (1) have a better understanding of ankle arthritis, (2) be able to demonstrate the potential for an improvement upon the current clinical examination for ankle misalignment and/or OA, and (3) provide evidence for, or against, the use of shoe inserts to manage and/or treat ankle misalignment and/or OA. It is hoped that this work will aid future clinicians and researchers in delaying or preventing the onset of ankle OA in at-risk veteran and non-veteran patients.

## List of Abbreviations

Provide a list of all abbreviations used in the protocol and their associated meanings.

AE – adverse event

CT – computed tomography

mSv - millisievert

OA – osteoarthritis

ROP – report of other problem

SAE – serious adverse event

UW/HMC – University of Washington/Harborview Medical Center

## 2.0 Introduction

The National Arthritis Data Workgroup that the 27 million US adults had clinical OA in 2008, with about 6% of the US population afflicted with ankle OA. In active duty military service, the rate of OA incidence is 7.86 cases per 1,000 person-years. Extremity and specifically ankle OA has been seen at a higher rate in Operation Enduring Freedom/Operation Iraqi Freedom (OEF/OIF) compared to previous conflicts. Concerning veterans, a VHA Support Service Center (VSSC) database search of local and national outpatients yielded the following table of ankle OA cases locally and nationally for 2014.

ICD - 9 Code	Entire VA	V20	Seattle VA
(715.17) Primary Ankle OA	1,087	186	21
(715.27) Secondary Ankle OA	300	31	2
(715.37) Unknown Primary / Secondary Ankle OA	7,165	258	175
(715.97) OA not Ankle Specific	8,434	334	102
(716.17) Traumatic Arthropathy of the Ankle	2,155	64	14

The majority of ankle OA is associated with post-traumatic injury. Incident rates for ankle sprains in the military have been reported at 45.14 per 1000 person-years between year 2000 and 2006; and at 34.95 per 1000 person-years in records between 1998 and 2006. Post-traumatic ankle injuries include: ankle fractures, recurrent ankle instability and single sprains with continued pain. The type of fracture is directly correlated to the incidence of OA: with increasing Weber fracture classification, there is an increase in OA incidence.

The average latency time between ankle trauma and end-stage OA is approximately 20.9 years. The mechanical stability of the ankle joint following fracture is essential to healthy function. Varus

misalignment of the hindfoot has been correlated with lateral ankle sprain or chronic lateral instability. It is important to note that misalignment is not only associated with prior trauma, of patients with primary (non-traumatic OA), 50% had no reported foot deformity, but 22% had cavovarus foot shape and 13% had planovalgus foot shape. These findings suggest that misalignment (traumatic or non-traumatic) may lead to OA over time.

Misalignment of the hindfoot can be observed in radiographic views of the supramalleolar, tibio-talar (intra-articular), and inframalleolar aspects. For the purposes of this proposal, tibio-talar misalignment is the focus. In a study of 406 ankles, 55% had varus alignment, 37% had neutral alignment and 8% had valgus alignment (normal alignment defined as between 90-99 degrees, varus alignment as less than 90 degrees and valgus alignment as 100 degrees or greater). In end-stage ankle OA patients, average alignments of 88.8 degrees(63–110 degrees) have been found, with 49.0% of cases having a varus malalignment, 50% within normal and 1% as valgus alignment. These studies show that varus misalignment has a significant presence in ankle OA, and is an important clinical diagnostic measure.

Joint-preserving surgeries (osteotomies of the tibia) have been explored to delay or prevent arthrodesis or arthroplasty by correcting alignment.; but conservative treatments also exist. Wedged insoles have been found to increase subtalar joint valgus moment in knee OA patients, and to alter ankle eversion and inversion moment. These studies suggest that wedged insoles could be used to modify the kinematics and kinetics of the ankle joint, potentially to a beneficial effect in ankle OA patients. However, it should be noted that all of these studies were unable to distinguish between subtalar and tibio-talar joint motion. This proposal's use of biplane fluoroscopy directly addresses that shortcoming.

### **3.0 Specific Aims and Hypotheses**

Clinically, tibio-talar alignment is assessed through static weight bearing radiographs – however, stance is functionally very different than gait and the tools to capture dynamic bone motion are not readily available in clinical settings. In research, optical motion capture (a technique that uses reflective markers and infrared cameras to track position and motion) is often used to study gait, however its ability to measure dynamic bone motion and position, in this case tibio-talar alignment, is limited. Biplane fluoroscopy is a radiographic technology that can track the talus, and thus measure dynamic ankle alignment. Importantly, some neutrally aligned ankles (determined via static radiographs) may actually exhibit misalignment during gait (dynamic biplane fluoroscopy). Treatment of misaligned ankles with conservative strategies (e.g., wedged insoles) may reduce misalignment, slowing the rate of OA development. We seek to quantify dynamic ankle misalignment in OA patients, detect a possibly hidden dynamically misaligned patient population, and explore how both populations respond to a conservative treatment approach.

**Specific Aim 1:** To investigate ankle kinematics in controls and participants with OA.

**Hypothesis 1:** During gait, there are different tibio-talar kinematics between participants with OA and static varus alignment, participants with OA and static valgus alignment, and controls.

**Specific Aim 2:** To identify dynamically misaligned ankles in participants with OA who are currently classified as neutrally aligned using static analysis.

**Hypothesis 2:** Some participants with OA and static neutral alignment will exhibit varus or valgus tibio-talar misalignment when measured dynamically using biplane fluoroscopy.

**Specific Aim 3:** To evaluate the potential of lateral or medial wedging to restore alignment in participants with OA and misaligned ankles.

**Hypothesis 3:** Participants with OA and static (varus/valgus) tibio-talar misalignment will exhibit reduced misalignment when walking with (lateral/medial) wedge insoles.

**Hypothesis 4:** Participants with OA and static neutral alignment, but with dynamic (varus/valgus) tibio-talar misalignment will exhibit reduced misalignment when walking with (lateral/medial) wedge insoles.

## **4.0 Resources and Personnel**

All data collection procedures for this study will be conducted at the VA Puget Sound in Seattle, WA. See Study Staff Sheet attachment for listing of personnel, ability to obtain consent, and access to PHI.

Under the supervision of the PI, designated study staff will be responsible for conducting recruitment, consent and scheduling study procedures. The PI, Investigators, and/or Research Engineers will conduct procedures with participants. The PI, Investigators, and the Biostatistician will be primarily responsible for data analysis and interpretation; Research Engineers may also assist with this. Under the supervision of the PI, the Program Coordinator is responsible for IRB related matters.

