### **Eligibility Screening and Group Determination**

Participants will have been preliminarily screened during recruitment, then during the first visit, after informed consent is obtained, we will make a final eligibility determination. This will include verifying that the information collected during recruitment is accurate and current.

At each visit that involves exposure to radiation female participants of child-bearing potential (under age 50) will undergo a pregnancy test (urine test) so we can verify that they are not pregnant. Designated study staff will escort female participants to the bathroom and provide them with a specimen cup, pregnancy test strip, and a disposable container on which to place the used test strip. Staff will go over the test instructions, and verify the test result. Staff will not handle urine specimens, we will tell participants how to handle and dispose of the materials. If the test indicates that the participant is pregnant she will be not be able to participate in the study and we will advise her to see her regular clinical care provider. If a participant cannot continue in the study they will still be compensated for the visit.

Participants with ankle OA will be grouped based on their clinical diagnosis of ankle coronal plane alignment (varus, neutral or valgus) as noted in their medical record, and/or determined by reviewing/measuring ankle alignment in x-rays in the medical record during recruitment and screening. Participants with ankle OA who do not have a formal clinical diagnosis of alignment type, if

alignment type cannot be determined via the x-rays on file, or if there are no x-rays on file, will be categorized after undergoing the Standing Long Leg X-ray.

Participant weight and height will be measured, and his/her age, sex, race/ethnicity and Veteran status will be recorded. Participants will be asked to walk in a straight line in the hallway while a researcher times the subject to determine his/her natural walking speed.

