### **Standing Long Leg X-ray**

If needed, this component will be performed at the VAPSHCS Department of Diagnostic Imaging. Participants will stand still while a frontal X-ray of the hips down is taken. This will allow us to quantify

the alignment at the hip, knee and ankle. We will also take standard foot alignment X-rays, including anterior/posterior and medial/lateral views of the feet.

We will measure the ankle alignment, if a participant is determined to have an ankle alignment type for which the study group is already full, that individual will not be able to participate further in the study, but will be compensated for the visit.

Please note, for participants that do not have a clinical diagnosis of alignment type (those with and without OA), we do not intend to inform them if we note misalignment. It is unknown at this time if ankle misalignment is causative to the development of ankle OA or if it is clinically relevant to prevention or conservative treatment of OA; these are some of the questions that this study hopes to address. Therefore, the information would not be useful to participants.

The CT scan and Biplane Fluoroscope session will be conducted in no particular order and may be conducted over multiple visits.

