### Biplane Fluoroscopy – Baseline

While wearing shorts (their own or ones we provide), participants will change into standard lab shoes and enter the Biplane Fluoroscopy Laboratory. Participants will step onto an elevated walkway, which is flat, about 3-feet wide, level, and has handrails on both sides. They will be asked to walk freely up and down the walkway to get comfortable with the test environment. External markers may be placed on the shoe for tracking purposes. While participants stand still on the platform, two fluoroscopes will capture simultaneous X-ray images of the participants' foot of interest, to record the standing position of the foot bones. These dual fluoroscopes allow for tracking of the bone motion in three dimensions (3D) while participants walk. Next, participants will be asked to walk along the platform while simultaneous X-ray images of the foot of interest are taken; each X-ray exposure is expected to last about 0.5 seconds, and will image from about 3 inches above the ankle to below the bottom of the shoe or foot. This set of standing and walking trials may also be

conducted with a neutral insert in the shoes, or barefoot. With some participants, we may capture images of each foot during the standing and walking X-ray procedures.

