#### Biplane Fluoroscopy – Wedged Insoles

Research staff will insert one of the wedged insole configurations (selected based on the participants' varus/valgus indication) into both of the participants' shoes. Participants in the control group may be asked to do these procedures with several different insole configurations. Participants will then repeat the standing trial, and then perform walking trials in the same format described above. With some participants, we may capture images of each foot during the standing and walking X-ray procedures. Participants will be instructed to let us know if they feel pain or discomfort during the procedures. If the shoes or inserts feel uncomfortable, we will attempt to re-fit them, if we are unable to achieve a comfortable fit, we will stop the procedures.

We will not ask participants to walk through our active fluoroscopic imaging system more than 80 times total during the entire study, and as noted above the total radiation exposure for the study will not exceed 0.47 mSv.

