### **Additional Analyses:**

1) Ankle misalignment likely varies during gait, and the pose of the foot during peak misalignment may not correlate with the position of the foot in the clinical 2D X-ray. To investigate this, the peak misalignment (varus or valgus) during gait as measured from the talar surface angles and talar tilt in data set 2 will be compared to the peak from the static standing fluoroscopic, this will be done for all groups. The result will be a measure of how frequently current clinical measure captures true maximum misalignment during gait.

2) The methods used to generate data set 2 can be used to re-create any 2D position from the 3D kinematics. Considering additional analysis 1, we may identify a phase of gait that more reliably demonstrates maximum misalignment (e.g. at heel rise). At the peak misalignment during that phase, we will generate additional simulated 2D X-ray images, in perspectives which would be possible to capture diagnostically (e.g. straight AP views and minor variations). In these new views, we will re-measure the talar surface angle and talar tilt. Such an exploration requires no additional subject X-ray exposure, as it is a digital processing of the data already collected. The result may be a 2D X-ray imaging angle / foot pose combination which is better suited than current methods for detecting maximum misalignment. This information may have immediate clinical benefit and will be rigorously pursued with additional study.

3) In a similar vein, we will perform a sensitivity test on the current clinical imaging methods. We will generate a series of 2D X-ray image planes by varying the standard clinical AP X-ray perspective in 1 degree increments about the SI and ML axes. Talar surface angle and talar tilt will be recalculated for each of these perspectives. By replicating this measure over a range of  $\pm 15$  degrees, we will determine the sensitivity of the clinical measure to foot positioning during diagnostic imaging.

The preceding three additional analysis serve to determine: (1) the ability of current methods to determine peak misalignment, (2) if a clinical angle / pose exists that is more diagnostically meaningful, and (3) the sensitivity of positioning to the current clinical method.

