from the UW, or any other facility, via the VA Release of Information Form will be transported from the UW by study staff and/or mailed to the VA. Prior to any analysis of the X-ray or CT data, all patient and institution identifiers will be removed from the headers of the radiograph files, and replaced with the study-unique code. When the de-identified copy of the X-ray and CT data is properly created, it will then be uploaded from the CD(s) to our computer workstation for further analysis. The CDs/DVDs will be stored in a locked cabinet in a locked office when not being processed. We will take the CD containing PHI to our VA IT manager to be destroyed. At no time, will copies of any medical image data containing patient identifiers be placed on any computer. The fluoroscopic images will be identified from the onset with the study code only (i.e., no PHI). Electronic transmission of de-identified fluoroscopy images will occur between the Biplane Fluoroscopy Laboratory data collection computer and the data processing computers in a different room at the VA. The de-identified images/data will also be kept indefinitely.

De-identified, non-sensitive electronic data with the study assigned codes (described above) and all 18 HIPAA identifiers removed or converted to de-identified format, may be stored on non-networked equipment at the VA Puget Sound (computers/laptops/sd cards). These devices are stored in locked areas. De-identified data files will be sent off-site to our biostatistician (VA research staff) [name], MS, and to our off-site collaborators [name] PhD and [name] PhD. De-identified electronic data will not be encrypted. De-identified data files will be sent via email and/or other electronic media (CD/DVD, thumbdrive via hand delivery or trackable mail) to our biostatistician and off-site collaborators. These non-sensitive files may also be transported on thumbdrives or non-networked laptops by staff working at both the VA and UW. De-identified data may be transmitted by email between study investigators and collaborators here and at UW and will not be secured. These data will be stored and used on electronic media.

De-identified data (as described above) will be stored and publicly accessible to search, retrieve, and analyze. Participants will be informed, via the consent form, about this additional use of data.

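### Staff who run the sessions also share in the analysis, and nothing in the published plan masks group or wedge condition during tracking, angle measurement or dynamic classification

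*Combined protocol and SAP*

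**What the plan says.** **Who does what.** Section 4.0 states: "The PI, Investigators, and/or Research Engineers will conduct procedures with participants". On analysis it states: "The PI, Investigators, and the Biostatistician will be primarily responsible for data analysis and interpretation; Research Engineers may also assist with this". Apart from the biostatistician, the same roles appear on both sides.

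**Who knows group and condition.** Under Biplane Fluoroscopy – Wedged Insoles (5.5), "Research staff will insert one of the wedged insole configurations", chosen by the participant's varus/valgus indication. Static class is taken from the medical record and/or "determined by reviewing/measuring ankle alignment in x-rays in the medical record during recruitment and screening" (Eligibility Screening and Group Determination). For the study films, the Standing Long Leg X-ray section says "We will measure the ankle alignment" and names no separate reader.

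**What the coding does.** In section 7.0, for x-ray and CT files, "all patient and institution identifiers will be removed from the headers of the radiograph files, and replaced with the study-unique code". Fluoroscopy files carry the study code from the start, so that they hold no protected health information. The stated purpose is privacy.

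**What the outcomes are.** Section 5.6 bases H1 and H3 on coronal plane alignment, and H2 on sorting statically neutral ankles into varus, valgus or neutral from fluoroscopy. H4 applies the H3 method to ankles that H2 reclassifies. No reader, masking step or numeric cut-off for dynamic class is given there.

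**The concern.** A study code hides a participant's name. It does not hide group, static class or wedge from a person who ran the session and then processes the files. The raw view may also reveal the condition, since each exposure "will image from about 3 inches above the ankle to below the bottom of the shoe or foot", so an insert could be visible.

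H2, H3 and H4 each state the result the team expects: some neutral ankles will prove misaligned in gait, and wedges will reduce misalignment. If a person's judgement enters tracking, angle measurement or classification, a small shift that follows group or condition adds to the estimated effect. More trials do not average it out.

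The exposure differs by hypothesis. In H2 the classification is itself the result, and it also decides who enters H4. H3 and H4 are within-subject contrasts with small standard errors, so a small shift counts for more. H1 asks only whether the groups differ, and its between-subject variance is larger.

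**Working it through.** **1. Setting the sections side by side.** Section 4.0 puts the session roles into the analysis. Section 5.5 shows that the session reveals indication and condition. Section 7.0 codes by participant. Section 5.6 adds no masking. The Quality Control section has the PI and/or research staff check the data by eye after each visit, also unmasked. The document does not say who tracks the bones, derives the angles or assigns the dynamic class, or how much of this is automated.

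**2. The plan's own power figure.** Inputs from 5.6, Power: OA mean -1.8, SD 1.8, 30 participants; controls mean 1.7, SD 2.9, 20 participants; 3 trials each; within-subject error 1.5 degrees; difference 3.5 degrees; p = 0.05 (two-sided assumed).
- Variance of a subject mean: OA 1.8² + 1.5²/3 = 3.99; controls 2.9² + 1.5²/3 = 9.16.
- SE = √(3.99/30 + 9.16/20) = 0.769.
- Power ≈ Φ(3.5/0.769 − 1.96) = 99.5%. Simulation of 5000 datasets gives 99.3% to 99.5%.

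The stated power above 99% is reproduced. Masking would not change it.

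**3. H3: what a reader shift would do.** Assumptions: no true wedge effect; 40 participants (the ceiling for each misaligned group); 3 trials in each condition; within-subject error 1.5 degrees; subject-by-wedge SD *s* from 0 to 1.0 degrees (not in the documents); two-sided 5% test on 39 df.
- SE = √((2 × 1.5²/3 + s²)/40).
- s = 0: √(1.5/40) = 0.194. s = 1.0: √(2.5/40) = 0.250.
- The probability of a significant result comes from the noncentral t with noncentrality shift/SE.

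| Assumed shift (degrees) | s = 0 | s = 1.0 |
|---|---|---|
| 0.1 | 8% | 7% |
| 0.25 | 24% | 16% |
| 0.5 | 71% | 50% |

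A larger *s* lowers these figures: at s = 1.5 the SE is 0.306, and a 0.5 degree shift gives 36%.

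**4. H1: the same 0.5 degree shift.** With the SDs in step 2 and a Welch test, simulation with no true difference gives 10% significant at 30 versus 20 participants and 12% at 40 versus 30 (SE = √(3.99/40 + 9.16/30) = 0.636).

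**5. H2.** Section 5.6 gives no cut-off for dynamic class, so the effect of a shift cannot be calculated. Only ankles close to a cut-off, on the side from which the shift crosses it, would change class.

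**The case against.** The strongest reply is that no human reading has been shown to be at risk. Section 4.0 speaks of analysis and interpretation, not of tracking or angle derivation, and the overlap is by role, not by named individual. Section 5.5 describes a CT-based bone model and 3D tracking, which may be largely automated. This stands as a limit: the concern applies only to whatever part needs judgement. It does not remove the gap, because no other role is given these tasks and automation is not described.

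A reader might take "In these new views, we will re-measure the talar surface angle and talar tilt" as proof that the H1-H4 angles are read by hand. It is not. That sentence belongs to exploratory item 2 of Additional Analyses, which uses a data set that the published text does not define. The measurement method may be set out elsewhere, so the finding is that no masking appears in this document.

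A reader might also infer that all four hypotheses are directional. H1 is not: it states a difference and is tested with an omnibus test. Nor do the documents establish that participants could not be kept unaware of the wedge. A neutral insert is allowed at baseline, and whether it could be told apart from a wedge is not discussed.

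Finally, masking applied only after tracking could come too late, because much of the judgement may already have been made. That is correct, and the fix has to reach tracking where it can.

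**Conclusion.** The concern holds as a risk that the plan leaves open and could reduce cheaply. Session roles share in the analysis, session staff know group and condition, coding protects identity only, and no masking of tracking, measurement or classification is stated. H2 is most exposed, together with the H4 population it selects, and then the H3/H4 wedge contrast. H1 is less sensitive.

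The percentages show sensitivity and do not predict bias. The documents give no size for a reader shift, and the H3 range rests on the assumed shift, the assumed subject-by-wedge SD, 3 trials per condition and full enrolment of 40. It would be wrong to conclude that bias is present, or that half or more of such studies would be falsely positive: 50-71% belongs to the 0.5 degree assumption alone, and at 0.1 degrees the rate is 7-8%. The stated power and sample size are unaffected.

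**What to change.** Add to section 5.6:

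1. Name the roles that track the bones, derive the angles and assign the dynamic class, and say which steps are automated.
2. Before any step that needs human judgement, including tracking where feasible, give every fluoroscopy trial a random code that hides participant, group, static class, footwear condition and trial order.
3. Where staffing allows, have tracking done by existing staff who did not run that session.
4. Compute the angles, or measure them on bone-only models or simulated views, from the coded files. Assign dynamic class by one rule fixed beforehand.
5. The biostatistician holds the key until angles and classes are locked.
6. State the residual limits. The insert may be visible during tracking, so masking of condition is partial there. OA changes may show on bone models, so masking of OA versus control is partial throughout.

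The cost is some file handling for every trial, a key-holder and a lock step. It needs no extra reader, imaging, visits or participants.
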